3. STUDY OBJECTIVES

3.1. Primary Objective

- To evaluate the clinical efficacy of apremilast 30 mg twice daily (BID) compared with placebo, in subjects with moderate to severe plaque psoriasis of the scalp, at Week 16

3.2. Secondary Objectives

The secondary objectives are:

- To evaluate the safety and tolerability of apremilast 30 mg BID compared with placebo, in subjects with moderate to severe plaque psoriasis of the scalp
- To evaluate the effect of apremilast 30 mg BID compared with placebo on itch over the whole body caused by plaque psoriasis
- To evaluate the effect of apremilast 30 mg BID compared with placebo on itch associated with plaque psoriasis of the scalp
- To evaluate the onset of effect on itch over the whole body caused by plaque psoriasis with apremilast 30 mg BID compared with placebo
- To evaluate the onset of effect on itch associated with plaque psoriasis of the scalp with apremilast 30 mg BID compared with placebo
- To evaluate the effect of apremilast 30 mg BID compared with placebo on health-related quality of life (HRQoL)

3.3. Exploratory Objectives

The exploratory objectives are:

- To evaluate the effect of apremilast 30 mg BID compared to placebo on Dermatological Life Quality Index (DLQI)

4. INVESTIGATIONAL PLAN

4.1. Overall Study Design and Plan

This is a Phase 3, multicenter, randomized, placebo-controlled, double-blind study of the efficacy and safety of apremilast (CC-10004) in subjects with moderate to severe plaque psoriasis of the scalp.

Approximately 300 subjects with moderate to severe plaque psoriasis of the scalp will be randomized 2:1 to receive either apremilast 30 mg BID or placebo for the first 16 weeks. Randomization will be stratified by baseline Scalp Physician Global Assessment (ScPGA) score (moderate [3], severe [4]) to ensure balance between treatment arms with respect to baseline severity of scalp psoriasis.

- Subjects randomized to the apremilast 30 mg BID treatment group will receive apremilast 30 mg tablets orally twice daily for the first 16 weeks
- Subjects randomized to the placebo treatment group will receive placebo tablets (identical in appearance to apremilast 30 mg tablets) orally twice daily for the first 16 weeks
- All subjects will receive apremilast 30 mg tablets orally twice daily after the Week 16 Visit through the end of the Apremilast Extension Phase of the study

The study will consist of four phases:

- Screening Phase – up to 35 days
- Double-blind Placebo-controlled Phase – Weeks 0 to 16

[figure not shown]
Subjects will receive treatment with one of the following:

- apremilast 30 mg tablets orally BID or
- placebo tablets (identical in appearance to apremilast 30 mg tablets) orally BID
- Apremilast Extension Phase – Weeks 16 to 32
 - All subjects will be switched to (or continue with) apremilast 30 mg BID at Week 16. All subjects will maintain this dosing through Week 32.
- Observational Follow-up Phase
 - Four-week Post-treatment Observational Follow-up Phase for all subjects who complete the study or discontinue from the study early.

After all subjects have completed the Week 16 Visit (or discontinued from the study), a Week 16 data restriction will be performed; the primary data analysis will be conducted [REDACTED] [REDACTED] [REDACTED] [REDACTED] [REDACTED]. However, unblinded data will only be made available to select Sponsor and Contract Research Organization (CRO) team members involved with analysis of the data [REDACTED] [REDACTED] [REDACTED]. All other Sponsor, site, and CRO personnel directly involved with the conduct of the study, will remain blinded to treatment assignments until the final database lock at the conclusion of the

study. At the end of the study, after all subjects have completed, or have been discontinued from the Apremilast Extension Phase (Weeks 16 to 32) and the Observational Follow-up Phase, the final analysis will be performed and a final Clinical Study Report will be generated.

Figure 1: Study Design

Abbreviation: BID = twice daily.

The study will be conducted in compliance with the International Council for Harmonisation (ICH) of Technical Requirements for Registration of Pharmaceuticals for Human Use/Good Clinical Practice (GCP) and applicable regulatory requirements.

4.2. Study Endpoints

The endpoints of the study are listed below:

4.2.1. Primary Endpoint

- Scalp Physician Global Assessment (ScPGA): Proportion of subjects with ScPGA score of clear (0) or almost clear (1) with at least a 2-point reduction from baseline at Week 16

4.2.2. Secondary Endpoints

- Itch NRS (Whole Body): Proportion of subjects with ≥ 4 -point reduction (improvement) from baseline in the whole body itch NRS score at Week 16
- Itch NRS (Scalp): Proportion of subjects with ≥ 4 -point reduction (improvement) from baseline in the scalp itch NRS score at Week 16
- Onset of effect on itch NRS (Whole Body): Proportion of subjects with ≥ 4 -point reduction (improvement) from baseline in the whole body itch NRS score by visit in placebo-controlled phase (Week 12, Week 8, Week 4, Week 2)

- Onset of effect on itch NRS (Scalp): Proportion of subjects with ≥ 4 -point reduction (improvement) from baseline in the scalp itch NRS score by visit in placebo-controlled phase (Week 12, Week 8, Week 4, Week 2)
- DLQI: Change from baseline in DLQI total score at Week 16

4.2.3. Exploratory Endpoints

CC

- ScPGA: Proportion of subjects with ScPGA score of clear (0) or almost clear (1) with at least a 2-point reduction from baseline by visit
- Itch NRS (Whole Body): Proportion of subjects with ≥ 4 -point reduction (improvement) from baseline in the whole body itch NRS score by visit in apremilast extension phase
- Itch NRS (Scalp): Proportion of subjects with ≥ 4 -point reduction (improvement) from baseline in the scalp itch NRS score by visit in apremilast extension phase

CC
C
I

 - DLQI: Change from baseline in DLQI total score at Weeks 4, 8, 16 and 32

CCI

4.2.6. Safety Endpoints

Safety endpoints will include:

- Adverse Events (AEs)
 - Type, frequency, severity, seriousness, and relationship of adverse events to apremilast

- Number of subjects who prematurely discontinue investigational product (IP) due to an adverse event
- Death
- Psoriasis flare
- Clinical laboratory evaluations
- Vital signs and weight
- Physical examinations
- Pregnancy tests for females of child bearing potential (FCBP)

4.2.7. Derivations of Efficacy Endpoints

The derivation of each efficacy endpoint is described below in separate sections. Baseline definition for all efficacy endpoints is given in Section 5.3. Change from baseline is calculated as on-treatment value minus the baseline value. Percent change from baseline is defined as $100^* \text{ Change from baseline/Baseline value (\%)}$. Handling of time points is described in Section 5.4.

4.2.7.1. Scalp Physician Global Assessment (ScPGA)

The ScPGA is a measurement of overall scalp involvement. The ScPGA is a 5-point scale that assesses three dimensions (Plaque Elevation, Scaling, and Erythema) on a scale of 0 (clear), 1 (almost clear), 2 (mild), 3 (moderate), to 4 (severe). The ScPGA scores will be collected on the eCRF directly at each visit.

For a post baseline visit, the ScPGA response is defined as achieving ScPGA global assessment of 0 (clear) or 1 (almost clear) with at least a 2-point reduction from baseline.

4.2.7.2. Whole Body Itch Numeric Rating Scale (NRS) Assessment

Prior to any other procedures or assessments being performed during the treatment period, the subject will be asked to assess their worst level whole body itch (including the scalp) over the past 24 hours and select a number on a scale of 0 to 10, where “0” represents no itching, and “10” represents the worst itch imaginable. The number selected by the subject will be recorded in the database.

The Whole Body Itch NRS scale has been validated among patients with moderate to severe plaque psoriasis, and a 4-point change from baseline was shown to be optimal for demonstrating a level of clinically meaningful improvement in itch severity.

For a post baseline visit, the whole body itch NRS response is defined as achieving ≥ 4 -point reduction (improvement) from baseline in the NRS score.

4.2.7.3. Scalp Itch Numeric Rating Scale (NRS) Assessment

After completing the Whole Body Itch NRS, the subject will be asked to assess the severity of their worst level of scalp itch over the past 24 hours and select a number on a scale of 0 to 10,

where “0” represents no scalp itch, and “10” represents the worst scalp itch imaginable. The number selected by the subject will be recorded in the database.

For a post baseline visit, the scalp itch NRS response is defined as achieving \geq 4-point reduction (improvement) from baseline in the NRS score.

4.2.7.4. Dermatology Life Quality Index (DLQI)

During the treatment phase, DLQI will be assessed by the subject upon arrival at the site, after completing the Whole Body Itch NRS, Scalp Itch NRS, **CCI** and prior to any other procedures or assessments being performed. The DLQI was developed as a simple, compact, and practical questionnaire for use in a dermatology clinical setting to assess limitations related to the impact of skin disease. The instrument contains 10 items dealing with the subject’s skin. With the exception of Item Number 7, the subject responds on a four-point scale, ranging from “Very Much” (score 3) to “Not at All” or “Not relevant” (score 0). Item Number 7 is a multi-part item, the first part of which ascertains whether the subject’s skin prevented them from working or studying (Yes or No, scores 3 or 0 respectively), and if “No,” then the subject is asked how much of a problem the skin has been at work or study over the past week, with response alternatives being “A lot,” “A little,” or “Not at all” (scores 2, 1, or 0 respectively). The DLQI total score is derived by summing all item scores, which has a possible range of 0 to 30, with 30 corresponding to the worst quality of life, and 0 corresponding to the best.

The developers suggest that the DLQI can be grouped into 6 subscales: symptoms and feelings; daily activities; leisure; work/school; personal relationships; and treatment. Scores for 4 of the subscales (symptoms and feelings, daily activities, leisure, and personal relationships) range from 0 to 6; scores for two of the subscales (work/school and treatment) range from 0 to 3. Higher scores correspond to poorer HRQoL.

[figure not shown]
[figure not shown]
[figure not shown]
If one of the 10 items is left unanswered, it is scored 0 and the scores are summed and expressed as usual out of a maximum of 30. If two or more of the ten items are left unanswered, DLQI total score will be left missing. When using sub-scales, if the answer to one item in a sub-scale is missing, the score is set to missing for that sub-scale.

DLQI total score and change from baseline will be derived, where change = visit value – baseline value.

[figure not shown]
[figure not shown]
CCI

CCI

[figure not shown]

CCI

CELGENE PROPRIETARY INFORMATION

CCI

4.2.9. Derivations of Safety Endpoints

Baseline definition for all safety endpoints is given in Section 5.3. Change from baseline is calculated as on-treatment value minus the baseline value. Handling of time points is described in Section 5.4.

4.2.9.1. Treatment-emergent Adverse Event

An AE is a treatment-emergent AE (TEAE) if the AE start date is

- On or after the date of the first dose of IP and no later than 28 days after the last dose of IP for subjects who have completed the study or have discontinued early by the time of database cut, or

- On or after the date of the first dose of IP for subjects who are ongoing at the time of database cut.

If the treatment-emergent status of an AE is unclear due to a missing/incomplete start date, it will always be considered treatment-emergent, unless shown otherwise by data. Date imputation rules for missing AE start dates are described in Appendices [Appendix A1A1.1](#) .

4.2.9.2. Treatment-emergent Adverse Events Leading to Drug Withdrawal, Leading to Drug Interruption, and Leading to Death, and Drug-related Treatment-emergent Adverse Events

A TEAE leading to drug withdrawal is a TEAE for which the investigator indicates that the action taken with respect to IP is withdrawn permanently. A TEAE leading to drug interruption is a TEAE for which the investigator indicates that the action taken with respect to IP is interrupted. A TEAE leading to death is a TEAE for which the outcome is fatal. Relationship to IP is based on the investigator's causality judgment; that is, a drug-related AE is an AE indicated by the investigator to have a suspected relationship to IP.

4.3. Randomization, Stratification, and Blinding

At Visit 2 (Week 0), subjects who meet entry criteria will be randomized using a permuted block randomization in parallel 2:1 to receive either apremilast 30 mg BID or placebo, using a centralized Interactive Response Technology (IRT). Designated research personnel at the investigational sites will be assigned password protected, coded identification numbers, which gives them authorization to enter the IRT to randomize subjects. Treatment assignment will be stratified by baseline ScPGA score [moderate (3), or severe (4)].

All subjects will receive apremilast 30 mg BID in the Apremilast Extension Phase.

The original treatment assignments (apremilast 30 mg BID or placebo) will remain blinded until all subjects have completed their Week 16 visit (or have discontinued). After Week 16 data restriction, unblinded data will only be made available to select Sponsor and CRO team members involved with analysis of the data ^{CC1} [REDACTED]. All other Sponsor, site, and CRO personnel directly involved with the conduct of the study, will remain blinded to treatment assignments until the final database lock.

4.4. Sample Size Determination

The sample size estimation is based on the results of the Phase 3 and 3b studies, including CC-10004-PSOR-008, PSOR-009 and PSOR-010 which demonstrated positive treatment effects between apremilast 30 mg BID and placebo in the proportion of subjects achieving ScPGA response at Week 16 (range 18% to 29%). Approximately 300 subjects will be randomized in a 2:1 ratio to apremilast 30 mg BID or placebo. With this sample size, a chi-square test at the 2-sided 0.05 significance level will have 90% power to detect a minimum treatment difference of 18% (38% for apremilast 30 mg BID versus 20% for placebo) between the two arms for

proportions of subjects achieving ScPGA response at Week 16 (defined as ScPGA score of clear [0] or almost clear [1] with at least a 2 point reduction from baseline at Week 16).

If at least 60% of the approximate 300 randomized subjects would be evaluable for the whole body itch NRS analysis, the subset sample size of 180 subjects will provide 90% power to detect a treatment difference of 25% (45% for apremilast 30 mg BID and 20% for placebo) in the proportion of subjects with ≥ 4 -point improvement from baseline in the whole body itch NRS score.

CELGENE PROPRIETARY INFORMATION

5. ANALYSIS PHASES OR PERIODS, DEFINITION OF ANALYSIS POPULATIONS, BASELINE AND TIME POINTS

5.1. Analysis Phases or Periods

For efficacy analysis, different phases will be used. For safety analysis, different phases and Apremilast-exposure Period will be used.

5.1.1. Analysis Phases

Per protocol specification, data summary and analysis will be provided for the following phases.

- Placebo-controlled Phase – Weeks 0 to 16

This phase starts on the day of randomization (Week 0/Visit 2), and stops on either: (1) the day the first IP for the next phase is dispensed at Week 16/Visit 7; or (2) the day of the discontinuation visit if the subject discontinued prior to or at Week 16/Visit 7; or (3) the last known study day if the subject is lost to follow-up prior to Week 16/Visit 7 during the phase.

For safety analysis in subjects who continued treatment in Apremilast Extension Phase (Weeks 16 to 32), the phase stopped one day prior to the first dose date in Apremilast Extension Phase.

- Apremilast Extension Phase – Weeks 16 to 32

This phase starts on the next day that the first IP is dispensed for the phase at Week 16/Visit 7, and stops on either: (1) the day of Week 32/Visit 10; or (2) the day of the discontinuation visit if the subject discontinued prior to or at Week 32/Visit 10; or (3) the last known study day if the subject lost to follow-up prior to Week 32/Visit 10 during the phase.

For safety analysis, the phase started at the first dose date in the phase.

- Observational Follow-up Phase – 4 weeks

For all subjects who complete the study or discontinue the study early, the Four-week Observational Follow-up Phase starts on the next day of the completion or discontinuation visit and stops at the follow-up visit or the last assessment date.

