## Appendix K: Treatment Schema for Dose Titration at Baseline

| Dose
Group                      | Day 1   |  | Day 2   |   | Day 3   |   | Day 4                                     |   | Day 5                                     |   | Days 6 -7                              |   |
|------------------------------------|---|--|---|---|---|---|---|---|---|---|--|---|
|                                    | AM  | PM   | AM  | PM  | AM  | PM  | AM  | PM  | AM  | PM  | AM                                     | PM  |
| Placebo
(dummy
titration)    | 10 mg
placebo
+ 20 mg
placebo
+ 30 mg
placebo    | 10 mg
placebo
+ 20 mg
placebo
+ 30 mg
placebo | 10 mg
placebo
+ 20 mg
placebo
+ 30 mg
placebo    | 10 mg
placebo
+ 20 mg
placebo
+ 30 mg
placebo    | 10 mg
placebo
+ 20 mg
placebo
+ 30 mg
placebo    | 10 mg
placebo
+ 20 mg
placebo
+ 30 mg
placebo    | 20 mg
placebo
+ 30 mg
placebo | 20 mg
placebo
+ 30 mg
placebo    |
| 30 mg
apremilast
(titration) | 10 mg
apremilast
+ 20 mg
placebo
+ 30 mg
placebo | 10 mg
placebo
+ 20 mg
placebo
+ 30 mg
placebo | 10 mg
apremilast
+ 20 mg
placebo
+ 30 mg
placebo | 10 mg
apremilast
+ 20 mg
placebo
+ 30 mg
placebo | 10 mg
apremilast
+ 20 mg
placebo
+ 30 mg
placebo | 10 mg
placebo
+ 20 mg
apremilast
+ 30 mg
placebo | 20 mg
placebo
+ 30 mg
apremilast | 20 mg
placebo
+ 30 mg
placebo | 20 mg
placebo
+ 30 mg
apremilast |

## Appendix L: Treatment Schema for Dose Titration at Week 16

| Dose
Group                           | Day 112  |  | Day 113  |  | Day 114  |  | Day 115                          |                                  | Day 116                          |                                  | Days 117 through 118             |                                  |
|---|--|--|--|--|--|--|----------------------------------|----------------------------------|----------------------------------|----------------------------------|----------------------------------|----------------------------------|
|   | AM   | PM   | AM   | PM   | AM   | PM   | AM                               | PM                               | AM                               | PM                               | AM                               | PM                               |

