5.3. Baseline Definitions

For efficacy analysis and summary of baseline disease characteristics data, baseline is defined as the last value measured prior to or at the randomization visit.

For safety analysis, baseline is defined as the last value measured prior to or on the day of the first dose of IP in the summaries for the Placebo-controlled Phase, and defined as the last value measured prior to or on the start day (defined in Section 5.1, ie, the first apremilast dose date) of the Apremilast-exposure Period in the summaries for the Apremilast-exposure Period. For subjects who are randomized but do not take any study medication, baseline for the Placebo-controlled Phase is defined as the last value measured prior to or on the day of the randomization.

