5.4. Time Points

Time points in all analyses are based on the remapped visits/study weeks using the following visit mapping algorithm, which may or may not be the same as the visits/study weeks as recorded in the database.

Post baseline time points in all analyses will be captured based on analysis visit window (range of study days) around the target day for each analysis visit, based on the actual day of evaluation relative to a reference date. Appropriate dates will be used to calculate the study day, e.g., date of measurement or date of specimen collection will first be used, and then the date of visits/study weeks as recorded in the database will be used. If there are multiple measurements within a time point based on the study day, then the non-missing value from the closest measurement to the planned study day will be used for that visit. If the value at a scheduled visit is missing and there is no value available within the time window based on the study day, the value at the study week will be missing.

Table 2: Table for Visit Mapping for by Time Point Analysis

Analysis Visit	Target Day	Visit Window
Baseline	1	≤ 1
Placebo-controlled Phase		
Week 2	15	2 – 21
Week 4	29	22 – 42
Week 8	57	43 – 70
Week 12	85	71 – 98
Week 16	113	99 – End of Phase
Apremilast Extension Phase		
Week 20	141	Start of Phase – 154
Week 24	169	155 – 196
Week 32	225	197 – End of Phase

Note: Target day and visit window are relative to the date of Visit 2/Week 0 (Day 1) for randomization. Definitions for baseline and start or end of the phases are specified in Section 5.1 and 5.3 for both efficacy and safety analysis.

Time points in the analyses or summaries of efficacy data over time include the scheduled study weeks per protocol, the end of a study phase, and the observational follow-up visit. Appropriate dates (e.g., date of measurement or date of specimen collection) will first be used to ensure only data (including data from scheduled, unscheduled, discontinuation, and observational follow-up visits) measured or collected within the specific analysis phase (as defined in Section 5.1) being analyzed or summarized are included, and then the visits/study weeks as recorded in the database will be used to assign one value (possibly missing) to each time point at the subject level. It is possible that multiple assessment values will fall into the same visit window. The following rule may be used to select the unique value for that analysis visit:

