1. Among all assessments in the same visit window for the analysis visit, select the value with the assessment date closest to the target day of the analysis visit;

2. If the relative days from 2 assessments are equally close to, but on different sides of the target day, then the latter assessment will be used for that analysis visit;
3. If multiple assessments are available on the same relative day, then the highest value of these assessments will be used for that relative day.

The time points for summaries of safety data (laboratory parameters, vital signs and weight) are based on study week/visit for the Placebo-controlled Phase. For the Apremilast-exposure Period, the scheduled study weeks for placebo subjects who are treated with apremilast 30 mg BID at Week 16/Visit 7 will be mapped to reflect the study weeks relative to the first dose of apremilast (see table below).

Table 3: Adjustment and Mapping of Study Weeks for Placebo Subjects who are Treated with Apremilast 30 mg BID after Week 16 in Summary of Safety Data over Time

Original Visit	Re-Mapped Visit for subjects initially randomized to placebo
Week 16 (Visit 7)	Week 0 (Baseline)
Week 20 (Visit 8)	Week 4
Week 24 (Visit 9)	Week 8
Week 32 (Visit 10)	Week 16

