11. SAFETY ANALYSIS

Safety will be assessed via descriptive statistics and point estimates. Unless otherwise specified, all safety analyses described in this section will be performed for both the Placebo-controlled Phase and the Apremilast-exposure Period. The safety analyses for the Placebo-controlled Phase will be based on the safety population and presented by treatment group (placebo, and apremilast 30 mg BID), and the safety analyses for the Apremilast-exposure Period will be based on the apremilast subjects as treated population and presented by apremilast dose group (i.e., apremilast 30 mg BID) irrespective of the start time of apremilast exposure (at Week 0 or 16).

For the analyses of AEs and marked abnormalities, the following point estimates are distinguished:

- Subject incidence: Subject incidence (i.e., percentage [%] used in a frequency summary) is defined as the number of subjects with the specific event divided by the number of subjects included in the analysis. Subjects with multiple occurrences of the specific event in the specific analysis period will be counted only once in the numerator.
- Exposure-adjusted incidence rate (EAIR) per 100 subject-years: The EAIR per 100 subject-years is defined as 100 times the number of subjects with the specific event divided by the total exposure time (in years) among subjects included in the analysis. Subjects with multiple occurrences of the specific event in the specific analysis period will be counted only once in the numerator. The exposure time for a subject without the specific event is the treatment duration, whereas the exposure time for a subject with the specific event is the treatment duration up to the start date (inclusive) of the first occurrence of the specific event. The total exposure time in years is calculated by dividing the sum of exposure time in days over all subjects included in the analysis by 365.25. The EAIR per 100 subject-years is interpreted as the expected number of subjects with at least one occurrence of the specific event per 100 subject-years of exposure to the IP.

AEs and marked abnormalities will be summarized by subject incidence and EAIR for the Placebo-controlled Phase (Weeks 0 to 16) and for the Apremilast-exposure Period. In addition, selected summaries for the Apremilast Extension Phase (Weeks 16 to 32) and the Observational Follow-up Phase (4 weeks) will be presented.

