11.3. Clinical Laboratory Evaluations

The endpoints for clinical laboratory evaluations include:

- Laboratory marked abnormalities (see [Appendix A2](#))
- Observed value and change from baseline over time in the following laboratory parameters
 - Hematology: hemoglobin, hematocrit, platelet, erythrocytes, leukocytes, basophils/leukocytes, eosinophils/leukocytes, lymphocytes/leukocytes, monocytes/leukocytes, neutrophils/leukocytes, basophils, eosinophils, lymphocytes, monocytes, and neutrophils
 - Serum chemistry: glucose, lactate dehydrogenase (LDH), bicarbonate, calcium, chloride, potassium, magnesium, phosphate, sodium, blood urea nitrogen, creatinine, urate, total cholesterol, high-density lipoprotein cholesterol (HDL-C), low-density lipoprotein cholesterol (LDL-C), triglycerides, alkaline phosphatase, AST (SGOT), ALT (SGPT), total bilirubin, albumin, and total protein
- Shifts from baseline to post-baseline time points and to the worst post-baseline value in terms of normal/abnormal (low or high) in the above hematology and serum chemistry parameters

Summary statistics of observed values and changes from baseline in laboratory parameters will be provided over time. Frequency summaries (shift tables) of shifts from baseline to post-baseline time points and to the worst post-baseline value in terms of normal/abnormal will be provided.

Laboratory marked abnormalities will be summarized; subject incidence and EAIR for each abnormality will be calculated based on subjects with a baseline value and at least one post-baseline value for criteria requiring baseline or subjects with at least one post-baseline value for criteria not requiring baseline. A subject data listing of laboratory marked abnormalities will be provided. Laboratory marked abnormalities will also be summarized for subjects with normal values at baseline and for subjects with abnormal values at baseline separately. For the purposes of these summaries, subjects with abnormal (normal) values at baseline are defined as those whose baseline value is low (not low) for criteria concerning low values and those whose baseline value is high (not high) for criteria concerning high values; both low and high are relative to the laboratory normal range.

A subject data listing of all laboratory data, including urinalysis, will be provided.

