11.4. Vital Signs and Weight

The endpoints for vital signs and weight include:

- Observed value and change from baseline over time in vital signs (temperature, pulse, and blood pressure)
- Shifts from baseline to post-baseline time points and to the worst post-baseline value in terms of normal/abnormal in pulse and blood pressure (normal ranges are defined as: 60-100 beats/minute for pulse, 90-140 mmHg for systolic blood pressure, and 60-90 mmHg for diastolic blood pressure)

- Observed value, change and percent change from baseline over time in weight

Summary statistics of observed values and changes from baseline in vital signs (including weight, for which percent change from baseline will also be summarized) will be provided over time. Frequency summaries (shift tables) of shifts from baseline to post-baseline time points and to the worst post-baseline value in terms of normal/abnormal will be provided for pulse and blood pressure.

Frequency summaries of change and percent change in weight from baseline to the end of the period will be provided by baseline BMI category (< 25 , ≥ 25 to < 30 , ≥ 30 to < 35 , ≥ 35 to < 40 , and ≥ 40 kg/m²) and by baseline weight category (< 70 , ≥ 70 to < 85 , ≥ 85 to < 100 , and ≥ 100 kg). The categories of weight change (kg) and percent change (%) are < -20 , ≥ -20 to < -10 , ≥ -10 to < -5 , ≥ -5 to < 0 , 0 , > 0 to ≤ 5 , > 5 to ≤ 10 , > 10 to ≤ 20 , and > 20 . The end-of-period or end-of-phase value is the last post-baseline value in the analysis period or phase (excluding the value obtained at the follow-up visit, if applicable) up to 28 days after the last dose of IP in the study.

A subject data listing of all vital signs and weight data will be provided.

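### The safety cut-off in SAP 5.1.1 puts Visit 7 labs and weight outside the Placebo-controlled Phase for subjects who take their first extension tablet on the visit day

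*SAP*

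**What the plan says.** SAP 5.1.1 gives the Placebo-controlled Phase two end rules. The general rule closes it on the day extension drug is dispensed at Visit 7, so Visit 7 is inside. The safety rule for subjects who continue is different: "the phase stopped one day prior to the first dose date in Apremilast Extension Phase". For safety, the Extension Phase then begins on that first dose date. The note to SAP Table 2 carries these boundaries over to safety: "Definitions for baseline and start or end of the phases are specified in Section 5.1 and 5.3 for both efficacy and safety analysis".

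Several safety outputs are defined within the phase:

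- SAP 11: "AEs and marked abnormalities will be summarized by subject incidence and EAIR for the Placebo-controlled Phase (Weeks 0 to 16"), and likewise for the Apremilast-exposure Period.
- SAP 11.3, for criteria that need a baseline: "subject incidence and EAIR for each abnormality will be calculated based on subjects with a baseline value and at least one post-baseline value". The other criteria still need a post-baseline value. The same section plans shifts to the worst post-baseline value.
- SAP 11.4, on weight: "The end-of-period or end-of-phase value is the last post-baseline value in the analysis period or phase".

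Two other rules bear on the same Visit 7 value. SAP 5.3 sets the baseline for the Apremilast-exposure Period as "the last value measured prior to or on the start day (defined in Section 5.1, ie, the first apremilast dose date"), and SAP Table 3 maps Visit 7 to Week 0 for placebo switchers. For by-visit tables, SAP 5.4 says: "The time points for summaries of safety data (laboratory parameters, vital signs and weight) are based on study week/visit for the Placebo-controlled Phase".

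**The concern.** The baseline rule has a same-day provision and the phase-end rule has none. So one Visit 7 blood draw can be pre-apremilast for the exposure baseline and yet too late for the placebo-controlled phase that it was meant to close.

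At stake is the only randomised safety comparison in the trial. If the rule is programmed literally, continuing subjects who dose on the visit day lose their Week 16 values from the phase-bounded laboratory and weight outputs. Early discontinuers are not subject to the day-before rule and keep their discontinuation-visit values. The more visit-day dosing there is, the more these tables describe people who stopped early. A programmer who follows the evident intent would keep the values, so two programmers could report different denominators from the same SAP.

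**Working it through.** **1. Date logic.** Let *v* be the Visit 7 day and *d* the first extension dose day. The safety phase ends on *d* − 1, so Visit 7 is inside only if *v* ≤ *d* − 1. SAP Table 2 target days follow 7 × week + 1: Week 8 = 57 and Week 16 = 113, as printed. The visit window is ±4 days.

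| Visit 7 day | First dose | Safety phase ends | Visit 7 inside? |
|---|---|---|---|
| 109 | 109 | 108 | No |
| 113 | 113 | 112 | No |
| 117 | 117 | 116 | No |
| 113 | 114 | 113 | Yes |

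The loss occurs exactly when the first dose is on the visit day.

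**2. Is visit-day dosing plausible?** It is not stated as a rule: the protocol says only that extension dosing follows the Week 16 visit. Nothing forbids it on the same day. Dosing is twice daily. Protocol Table 3 has the old tablets returned and counted, and new ones dispensed, at Visit 7. The protocol's "Appendix L: Treatment Schema for Dose Titration at Week 16" heads its first dosing column Day 112, against a Visit 7 target of Day 113. Next-day dosing on the SAP's count would be Day 114.

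**3. What remains in the phase for an affected subject.**

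- *Weight.* The row in Protocol Table 3 has 11 marks for 11 visits: Screening, Weeks 0, 8, 16, 24, 32 and follow-up. Without Week 16, the last scheduled value is Week 8: 113 − 57 = 56 days earlier, or 8 of the 16 weeks.
- *Vital signs.* Weeks 2, 4, 8 and 12 remain, so 1 of 5 scheduled post-baseline values is lost.
- *Labs.* The row is damaged, with 12 marks for 11 visits: X X - - - - - X - - X -. Removing each mark in turn gives:

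| Mark removed | Scheduled draws after Week 0 |
|---|---|
| Any of 1-7 | Week 16, Week 32 |
| 8 | Week 32 |
| 9 or 10 | Week 20, Week 32 |
| 11 | Week 20 |
| 12 | Week 20, follow-up |

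No alignment puts a draw at Weeks 2 to 12. Only the first gives the planned placebo-controlled lab tables any scheduled on-treatment data. It also agrees with Protocol 6.2.1 (labs at end of treatment) and 6.3 (none at follow-up). On that reading, an affected subject with no unscheduled draw has no post-baseline lab value in the phase, and leaves both numerator and denominator of the marked-abnormality table.

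**4. Difference between arms.** For an affected placebo subject, the Visit 7 value is outside the Placebo-controlled Phase and is the baseline of the Apremilast-exposure Period. An abnormality that arose on placebo and is first seen at Visit 7 therefore counts in neither main table. For an affected apremilast subject, the same value is post-baseline in the Apremilast-exposure Period and counts there.

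**5. How many subjects.** The documents do not give the share *s* of continuing subjects who dose on the visit day. Assume 80-90% of 300 continue (0.8 × 300 = 240; 0.9 × 300 = 270), split 2:1, with the same *s* in both arms. Affected = *s* × continuing:

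| *s* | All | Apremilast | Placebo |
|---|---|---|---|
| 0% | 0 | 0 | 0 |
| 25% | 60-68 | 40-45 | 20-23 |
| 50% | 120-135 | 80-90 | 40-45 |
| 100% | 240-270 | 160-180 | 80-90 |

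**The case against.** The strongest reply is that the trigger is undocumented. No text places the first extension dose on the visit day, and with next-day dosing nothing is lost. Day 112 in Appendix L is one day before the Visit 7 target and may simply be 16 × 7. This stands as a limit on size: the range properly starts at zero, and Appendix L is suggestive only. It does not remove the gap, because the rule gives the wrong result for any subject who doses that day.

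Second, the lab consequence rests on a broken row. The DLQI row, checked against the SAP's DLQI weeks (4, 8, 16 and 32), has its surplus cell among cells 8-10. On that alignment the lab mark in cell 8 would be surplus or Week 20. A Week 20 and Week 32 reading also agrees with Protocol 6.2.1 and 6.3. This stands in part: Week 16 labs are an inference. But the physical-examination row has its surplus elsewhere, after the Visit 10 mark, so one row's alignment does not fix another's. A Week 20 reading would leave the planned placebo-controlled lab tables with no scheduled on-treatment data. The weight consequence does not depend on this row.

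Third, SAP 5.4 keys by-visit safety tables to study week, the values remain in listings, and safety is descriptive. This is accepted for by-visit tables and listings. That sentence governs time points, though, and does not move the phase end used for marked abnormalities, worst-value shifts or end-of-phase weight.

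Finally, keeping Visit 7 labs while treatment duration ends the day before leaves a one-day mismatch in exposure-adjusted rates. That is true but negligible: about one day in 112, and exposure can be capped at treatment duration.

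**Conclusion.** The concern holds for subjects who take the first extension dose on the Visit 7 day, in outputs bounded by the phase. This is a stated rule giving a wrong result, and it should be corrected before unblinding.

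- **Firm:** the date logic, the conflict with the same-day baseline rule, and the 56-day fallback of end-of-phase weight.
- **Inferred:** that Week 16 is the only scheduled on-treatment lab draw in the phase.
- **Assumed:** 80-90% continuation, and a visit-day share anywhere from 0 to 100%, giving 0 to 240-270 affected subjects.

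No change in any incidence can be computed from the documents. Efficacy analyses are not affected, because the general rule keeps Visit 7 inside the phase. Confidence is medium.

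**What to change.** Add to SAP 5.1.1:

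> For laboratory, vital-sign and weight data, the Placebo-controlled Phase ends on the later of (a) the Week 16/Visit 7 assessment date, if on or before the first extension dose date, and (b) the day before the first extension dose. Visit 7 assessments made on the first extension dose date count in the Placebo-controlled Phase; the Extension Phase takes only later assessments.

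Unscheduled draws between Visit 7 and a later first dose then stay in the Placebo-controlled Phase. Keep the day-before rule for adverse events and treatment duration. Visit 7 values may still serve as the Apremilast-exposure baseline for placebo switchers.

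Align the SAP Table 2 note with the new text. In the same edit, say that by-visit safety tables follow study week/visit, since SAP 5.4 also states that all analyses use the remapped windows.

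Cost: two sentences in SAP 5.1.1 and one edit to the Table 2 note. No new data are needed, and dosing and visit conduct do not change.
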